# 4.2. PP PRIMARY EFFICACY OBJECTIVE: RESPONSE AT 56 DAYS

Table 41: Primary Efficacy Objective. Day 56 Evaluation. PP

intracranial Evaluation at 56 days	
CR	
PR	
SD	
PD	
NE	

Table 42: PP: intracranial Objective Response Rate at 56 days

All patients: ORR intracranial response	
CR or PR	
SD or PD	

All patients: ORR intracranial response
NE
Total
Cohort 1: ORR intracranial response
CR or PR
SD or PD
NE
Total
Cohort 2: ORR intracranial response
CR or PR
SD or PD
NE
Total

# **4.2.1.INTRACRANIAL RESPONSE DURATION**

Table 43: Intracranial Response Duration (months) ITT

Duration of response (months)	
_ N	
Mean (95%CI)	
SD	
Median (95%CI)	
Range	

Table 44: Intracranial Response Duration (months) PP

Duration of response (months)	
N	
Mean (95%CI)	
SD	
Median (95%CI)	
Range	

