# 10.2. Study endpoints

Intracranial objective response (iORR) rate by modified RECIST 1.1 before local treatment in cohort 1 and 2: iORR calculated as the proportion of patient with a best overall intracranial response of complete response (CR) or partial response (PR) before local treatment in cohort 1 and 2. The final statistical analysis of this endpoint is expected to be performed within 3 months after the local treatment of the last patient in any cohort. iORR will be also reported separately for both cohorts.

**Duration of intracranial response in both cohorts (iDOR):** Calculated as the time from the date of first documented CR or PR to the first documented intracranial progression or death due to underlying cancer, in patients with documented intracranial CR or PR before local treatment. The final statistical analysis of this endpoint is expected to be performed within 6 months after database closure expected at 24 months after last patient inclusion, however interim analysis might be performed when analysing other primary variables.

The intracranial progression free survival (iPFS) by modified RECIST in both cohorts: iPFS is defined as the time from the date of inclusion to the date of the first documented intracranial disease progression or death due to any cause, whichever occurs first. PFS will be determined based on tumour assessment (modified RECIST version 1.1 criteria). The local Investigator's assessments will be used for analyses. Those patients who are alive and have not progressed at the last follow-up, date of progression will be censored at the date of the last follow-up. Patient with no additional image test other than baseline will be censored to the day after to inclusion. The final statistical analysis of this endpoint is expected to be performed within 6 months after database closure expected at 24 months after last patient inclusion, however interim analysis might be performed when analysing other primary variables.

Percentage of patients free of intracranial progression at 6 (week 24), 12 (week 48) and 24 months (week 96) in both cohorts: percentage of patients free of intracranial progression assessed by modified RECIST at 6 months (week 24), 12 months (week 48) and 24-month (week 96) considering date of inclusion. The final statistical analysis of this endpoint is expected to be

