#### 10.6. Statistical analysis

For each categorical variable, the results will be summarized by frequencies and percentages. For each continuous variable, the results will be summarized by descriptive statistics such as median, range, and interquartile range or by means, standard deviations and 95% confidence intervals (CIs). For proportions, point estimates and exact 95% confidence intervals will be calculated. For time to event endpoints, Kaplan-Meier estimates at selected time points and corresponding curves will be presented. Time to event is derived relative to the first study treatment administration. Laboratory values will be expressed as the absolute values and as grading (ordinal categorical variables) according to NCI CTCAE v 4.03.

Treatment-emergent AE (AEs starting after the administration of study treatment and up to study completion) will be summarized by system organ class and preferred term. Grading will be presented by type and grade in tables showing frequency and percentage of the within-patient worst grades. In addition, grade ≥3 AEs will be summarized separately. Full analysis details will be outlined in the statistical analysis plan (SAP).

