# 3.5. TREATMENT COMPLIANCE

Upon database closure, there are 4 patients still undergoing treatment.

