# 4.5. INTRACRANIAL OVERALL SURVIVAL (IOS). 4.5.1.ITT ALL PATIENTS: INTRACRANIAL OVERALL SURVIVAL (IOS).

Table 54: Events type OS

os	N	%	95%CI
Alive			
Death			
Total			

Table 55: Median/mean OS (estimated by Kaplan-Meier)

	Median (months)	CI 95%	Mean	CI 95%
Overall survival				

Table 56: OS estimated survival ratio

os	Events (%, total N)	Patients at risk	% estimated cumulative survival ratio	CI 95%
At 6 months At 12 months At 18 months At 24 months				

Figure 5: Overall survival

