# 4.6. INTRACRANIAL PROGRESSION-FREE SURVIVAL (IPFS).

Intracranial Progression-free survival (PFS), defined as the time from inclusion (first dose of treatment) until intracranial tumour progression (RECIST 1.1) or death. Patients without any of the previous events are censored at the date of the last available tumor assessment.

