#### 7.3.1.INTRACRANIAL RESPONSE DURATION

Table 167: Intracranial Response Duration (months)

Duration of response	
(months)	
N	
Mean (95%CI)	
SD	
Median (95%CI)	
Range	

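### SAP Tables 43, 44 and 167 summarise duration of intracranial response as a plain continuous variable instead of by the Kaplan-Meier method of protocol 10.6, and neither document gives a censoring rule for it

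*Combined protocol and SAP*

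**What the plan says.** Protocol 10.2 defines iDOR among responders as follows: "Calculated as the time from the date of first documented CR or PR to the first documented intracranial progression or death due to underlying cancer". Protocol 10.6 sets the method for this kind of endpoint: "For time to event endpoints, Kaplan-Meier estimates at selected time points and corresponding curves will be presented".

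The SAP tabulates iDOR three times: "Table 43: Intracranial Response Duration (months) ITT" and "Table 44: Intracranial Response Duration (months) PP" in SAP 4.2.1, and Table 167 in SAP 7.3.1. Each shell has the same rows: N, mean with 95% CI, SD, median with 95% CI, and range. Age and weight have the same layout in SAP 3.2.

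Where the SAP intends Kaplan-Meier it generally names it, as in the title "Table 55: Median/mean OS (estimated by Kaplan-Meier". For intracranial progression-free survival (iPFS), SAP 4.6 also gives a censoring rule: "Patients without any of the previous events are censored at the date of the last available tumor assessment". SAP 4.7 repeats that rule for extracranial progression-free survival (ePFS). Neither document has a corresponding sentence for iDOR.

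**The concern.** A responder whose response is still ongoing when observation stops contributes only a lower bound on duration. A table of N, mean, SD and range cannot represent that. Whoever fills it must either leave the patient out or enter the truncated time as if the response had ended, and the SAP does not say which.

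Durability is central to this trial. Section 3 of the protocol asks whether local therapy after an incomplete response could lengthen responses, and iDOR is the secondary endpoint that addresses this most directly. A duration that ignores censoring could not fairly be set beside Kaplan-Meier durations from other trials. It would also depart from the trial's own protocol.

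**Working it through.** **1. The shells side by side**

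| Endpoint (SAP tables) | Event/censored counts | Kaplan-Meier named | Curve | Censoring rule |
|---|---|---|---|---|
| iDOR (43, 44, 167) | none | no | none | none in either document |
| OS (54-56) | alive/death | in table title | yes | not written out |
| iPFS (72-74) | yes | in heading and footnote of the time-point table | yes | SAP 4.6 |
| ePFS (90-92) | yes | in table title | yes | SAP 4.7 |

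**2. Can responders be censored under this design?** Four features make it plausible.
- SAP 3.5 reports: "Upon database closure, there are 4 patients still undergoing treatment". The SAP does not say whether these patients are responders. Against the planned 63 they are 4/63 = 6%.
- Protocol 5.3 moves patients to survival-only follow-up after progression. A responder who progresses only outside the brain can therefore leave intracranial assessment with the response ongoing.
- Protocol 8.2(f) ends formal follow-up, apart from date of death, for patients who switch treatment.
- Under protocol 10.2, deaths not due to the cancer are not iDOR events.

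**3. Size of the effect (illustration).** The plan states no expected duration, so there is no figure of its own to reproduce. Assumptions: exponential durations, true median m = 10 months, so the true mean is 10/ln 2 = 14.4. The simulation used 38 responders (60% of 63 = 37.8). With n = 38 the average uncensored sample median is already about 10.2, so compare the simulated medians below with 10.2.

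*(a) Independent exponential censoring of a fraction c.* The observed time min(T, C) is exponential with median m(1 - c), and so is the observed time among events alone. Dropping censored responders and counting them as ended therefore have the same effect.

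| c | m(1 - c) | Simulated plain median |
|---|---|---|
| 10% | 9.0 | about 9.2 |
| 20% | 8.0 | about 8.1 |
| 30% | 7.0 | about 7.1 |
| 40% | 6.0 | about 6.1 |

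The Kaplan-Meier median in the same simulations is 10.2 to 10.5.

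*(b) Administrative censoring only.* Thirty-six months of recruitment (protocol 8.3) and closure 24 months after the last inclusion (protocol 10.2) give follow-up spread over 24 to 60 months, ignoring the roughly 2 months to first response. With λ = ln 2/10 = 0.0693:
- Fraction censored = (e^(-24λ) - e^(-60λ))/(36λ) = (0.1895 - 0.0156)/2.495 = 0.070.
- Mean, counted as ended = 14.4 × (1 - 0.070) = 13.4, against 14.4.
- Median, counted as ended: every censoring time is later than the true median, so it is unaffected (simulated about 10.2).
- Median, censored dropped: simulated about 9.2.

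The counted-as-ended mean is low in both settings. The median is low if censored responders are dropped, or if censoring comes before the median.

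**The case against.** The strongest reply is that protocol 10.6 still governs and nothing in the SAP withdraws it. The row for the median with its CI could hold a Kaplan-Meier median. A mean row proves nothing, because the SAP reports Kaplan-Meier means for OS. The median iPFS tables (for example Table 73) carry no Kaplan-Meier label either. All of this stands. It leaves the SD and the range, which have no ordinary Kaplan-Meier reading, together with the missing counts, curve and censoring rule. That is enough to show that the shell does not implement 10.6.

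A reader might go further and infer that the SAP drops censored responders or counts them as ended, so that the trial's duration is biased low. The documents do not support that as fact. The handling is not stated, and the 10 to 40% censoring rates are assumed. The only count offered, the 4 patients on treatment, is not tied to response, and treatment can continue after progression with the sponsor's agreement.

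The bias may also be small. The nearest figure in the documents is the 5.6-month progression-free survival cited from the dabrafenib-trametinib brain metastasis trial. With a true median of 6 months and administrative censoring only, about 1.4% would be censored, and the plain median would be 6.1 (counted as ended) or 6.0 (dropped). If every responder had an event there would be no bias. Kaplan-Meier iPFS also covers part of the durability question.

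**Conclusion.** The point holds as a departure from the protocol and a gap in specification. Three SAP shells present a time-to-event secondary endpoint in a form that cannot show censoring, contrary to protocol 10.6, and no iDOR censoring rule exists. The consequence is conditional. If any responder is censored, the plain mean is too low. The plain median is too low if censored responders are dropped or if censoring comes early, and it is essentially right if censored times are counted as ended and all of them fall after the median.

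For a true median of 10 months the illustrated effect on the median runs from none to about 4 months. It rests on assumed exponential durations and assumed censoring patterns. The primary intracranial response rate is not touched. The change should be made, but it does not threaten the trial's main conclusion.

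**What to change.** 1. Replace Tables 43, 44 and 167 with: number of responders, events, censored, Kaplan-Meier median with 95% CI, Kaplan-Meier rates at stated time points, and a curve. The iPFS layout is a starting point, but its 3, 6 and 12 months should not be copied without thought; 6, 12 and 24 months from first response would be one choice. State the time origin, because protocol 10.6 counts from first treatment whereas 10.2 starts iDOR at first response.
2. Delete the SD, the range, and any mean not estimated by Kaplan-Meier.
3. State that responders without an event are censored at the last evaluable brain MRI, in line with SAP 4.6. Protocol 10.2 censors iPFS at last follow-up instead, so reconcile the two. Define evaluable as allowing a judgement on progression, since protocol 10.3 treats lesions as non-evaluable after local treatment but keeps MRI for detecting progression.
4. State how deaths not due to the cancer are handled (censored or competing event), with death from any cause as a sensitivity analysis.

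The cost is three table shells, two written rules and the matching programming. The definition of iDOR already requires the dates of response, progression and death and the cause of death, so no new data are needed. Because the SAP already refers to database closure, date the change and record the reason.

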# 4.3. RADIOTHERAPY TREATMENT

### **ITT: RADIOTHERAPY TREATMENT**

Table 45: Radiotherapy treatment. ITT

Radiotherapy treatment (Local and/or Whole Brain)  N  Yes	
Yes	
Yes (CR) 	
No	
No (CR)	
LocaL Radiation treatment	
N	
Yes	
Yes (CR)	
No	
No (CR)	
Local Radiation Treatment type	
N	
No	
Radiosurgery (RS)	

Stereotactic radiosurgery (SRS)	
Device Used	
Missing	
N	
Gamma Knife	
Accelerator Linac-Based Systems (IMRT, Rapid Arc, VMAT)	
Cyberknife	
Whole Brain Radiotherapy	
N	
Yes	
No	
No (CR)	

# **PP: RADIOTHERAPY TREATMENT**

Table 46: Radiotherapy treatment. PP

Radiotherapy treatment (Local and/or Whole
Brain)
N
Yes
Yes (CR) 
No
No (CR)
Local Radiation treatment
N
Yes
Yes (CR)
No
No (CR)
Local Radiation Treatment type
N
No
Radiosurgery (RS)
Stereotactic radiosurgery (SRS)
Device Used
Missing
N
Gamma Knife
Accelerator Linac-Based Systems (IMRT, Rapid Arc, VMAT)

Cyberknife	
Whole Brain Radiotherapy	
N	
Yes	
No	
No (CR)	

# 4.3.1.ALL PATIENTS: DETAILS OF LOCAL RADIATION TREATMENT

Table 47: Details of local radiation treatment

Patient Coho Intention to LocaL Radiation Number rt population treatment type Local Radiation Treatment type	Whole Brain Radiotherapy Radiotherap treatment (Local y and/or Whole Brain)
--	---

# 4.4. LAST STATUS

Table 48: Arithmetic median for all patients

Overall	
Overall follow-up since cancer diagnosis: all	patients (months)
N	
Mean (95%CI)	
SD	
Median (95%CI)	
Range	

Table 49: Arithmetic median for alive patients

Overall	
Global follow-up since cancer diagnosis: patients alive (moths)	
N	
Mean (95%CI)	
SD	
Median (95%CI)	
Range	

Table 50: Follow-up since cancer diagnosis based on reverse censoring (months)

	Median	95%CI
Reverse censoring		

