performed within 6 months after database closure expected at 24 months after last patient inclusion, however interim analysis might be performed when analysing other primary variables

Percentage of patients (%) free of extracraneal progression at 6 (week 24), 12 (week 28) and 24 months (week 96): percentage of patients free of progression by RECIST 1.1 at 6 months (week 24), 12 months (week 48) and 24-month (week 96) considering date of inclusion. The final statistical analysis of this endpoint is expected to be performed within 6 months after database closure expected at 24 months after last patient inclusion, however interim analysis might be performed when analysing other primary variables.

**Overall Survival in both cohorts (OS):** OS is calculated as the time from date of inclusion to date of death due to any cause. The final statistical analysis of this endpoint is expected to be performed within 6 months after database closure expected at 24 months after last patient inclusion, however interim analysis might be performed when analysing other primary variables.

Percentage of patients (%) alive at 6, 12 and 24 months in both cohorts: percentage of patients alive at 6 months, 12 month and 24-month considering date of inclusion. The final statistical analysis of this endpoint is expected to be performed within 6 months after database closure expected at 24 months after last patient inclusion, however interim analysis might be performed when analysing other primary variables.

**Toxicity of the combination until local treatment:** Number of patients with adverse events and serious adverse events, changes in laboratory values, vital signs, electrocardiograms (ECGs), LVEF (MUGA (Multigated Acquisition Scan) / echocardiogram) and assessment of physician, dermatological and ocular examinations graded according to the National Cancer Institute (NCI) Common Terminology Criteria for Adverse Events (CTCAE) v 4.03 until local treatment (local treatment D1). It will be studied using descriptive statistics techniques, such as frequency tables and contingency tables. The final statistical analysis of this endpoint is expected to be performed within 6 months after database closure expected at 24 months after last patient inclusion, however interim analysis might be performed when analysing other primary variables.

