### Figure: intracranial Progression Free Survival (PP Cohort 2)

# 4.7. Extracranial Progression-free survival (ePFS).

Extracranial Progression-free survival (PFS), defined as the time from inclusion (first dose of treatment) until extracranial tumour progression (RECIST 1.1) or death. Patients without any of the previous events are censored at the date of the last available tumor assessment.

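### SAP Tables 48–50 count follow-up from cancer diagnosis, while OS, iPFS and ePFS start at inclusion or first dose, so the median would overstate follow-up if read as trial follow-up

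*Combined protocol and SAP*

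**What the plan says.** SAP 4.4 (Last status) contains three follow-up summaries, all with the same origin:

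- Table 48, all patients: "Overall follow-up since cancer diagnosis: all".
- Table 49, survivors: "Global follow-up since cancer diagnosis: patients alive (moths".
- Table 50, the reverse-censoring median: "Table 50: Follow-up since cancer diagnosis based on reverse censoring (months".

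The SAP does not define the diagnosis meant. It tabulates two separate intervals up to treatment start: from first diagnosis (Tables 13–14) and from diagnosis of the current melanoma (Tables 23–24).

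The survival-type endpoints start elsewhere:

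- OS, protocol 10.2: "OS is calculated as the time from date of inclusion to date of death due to any cause". SAP 4.5 states no origin for OS, so the protocol governs.
- iPFS, protocol 10.2: "iPFS is defined as the time from the date of inclusion to the date of the first documented intracranial disease progression or death".
- iPFS, SAP 4.6: "defined as the time from inclusion (first dose of treatment) until intracranial tumour progression (RECIST 1.1) or death".
- ePFS, SAP 4.7: "defined as the time from inclusion (first dose of treatment) until extracranial tumour progression (RECIST 1.1) or death".
- General rule, protocol 10.6: "Time to event is derived relative to the first study treatment administration".

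No table in the SAP or its add-on analyses summarises follow-up from inclusion or first dose. Table 53 lists dates patient by patient but does not summarise them.

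**The concern.** A median follow-up tells the reader how long patients were observed for the endpoint beside it, so it has to be on that endpoint's time scale. Time between diagnosis and inclusion is not observation in this trial, and every included patient necessarily survived it. Adding it to follow-up adds months in which an on-study death was impossible.

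The interval may be long for some patients. Protocol 6.1 admits patients after prior immunotherapy, and patients who relapsed at least 12 months after ending adjuvant BRAF with or without MEK inhibitors. The SAP plans OS and ePFS estimates out to 24 months. A follow-up median counted from diagnosis and printed in the same report could be taken as the length of observation behind those estimates.

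**Working it through.** **No plan figure to reproduce.** The SAP tables are empty shells, so the check is on direction and on a range of possible sizes.

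**Direction.** Protocol 6.1 requires a histologically confirmed diagnosis at entry, so diagnosis precedes inclusion. For each patient:

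follow-up from diagnosis = follow-up from inclusion + (inclusion date − diagnosis date).

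The last term is not negative. No patient's follow-up can be shorter from diagnosis, and neither can the simple medians in Tables 48 and 49. The reverse Kaplan-Meier median (Table 50) is not tied to this rule patient by patient, but it was longer in every scenario below.

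**Inputs from the documents.** Recruitment 36 months and follow-up 24 months (protocol 8.3); database closure 24 months after last inclusion (protocol 10.2); median survival of about 9 months with treatment (protocol 2.3), used as the low end.

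**Assumptions.** Uniform accrual; exponential OS with median 9, 12 or 18 months; no loss to follow-up; an assumed diagnosis-to-inclusion interval, since the documents give none.

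**Median from inclusion.** Potential follow-up is 24 + 36U months, with U uniform on 0 to 1. Its median is 24 + 36 × 0.5 = 42 months. Simulation with 20,000 patients per scenario gave 41.0 to 42.5. Protocol 8.1 can also be read as ending OS contacts at 24 months per patient, and the median is then 24.

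**Median from diagnosis, constant interval.** If every patient has the same interval L, all times shift by L. With L = 12 the median is 42 + 12 = 54 months.

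**Median from diagnosis, varying interval.** With exponential intervals and no delayed-entry correction, the reverse Kaplan-Meier medians in months were as follows (range over the three OS medians):

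| Assumed median interval | Followed to data cut (about 42 from inclusion) | Capped at 24 months (24 from inclusion) |
|---|---|---|
| 1 month | 43.4–43.7 | 25.1–25.2 |
| 3 months | 47.2–48.2 | 27.6–28.4 |
| 6 months | 53.6–59.1 | 32.6–37.0 |
| 12 months | 69.2–106.9 | 45.1–65.0 |

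**Why the excess can exceed the interval.** Patients with long intervals sit in the risk set before they are on study, and the same interval enters both their death time and their censoring time. The estimator then falls too slowly.

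**Simple median (Table 48).** With OS median 12 months and follow-up to the data cut, it moves from about 12 months to about 17 for a 3-month interval and about 29 for a 12-month interval.

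**The case against.** The case for leaving the tables alone has four parts.

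1. **The origin is stated openly.** The labels name diagnosis, and nothing in the documents says these tables will be used to judge the maturity of OS or iPFS. This stands: the overstatement arises only if the figure is read as trial follow-up. With no inclusion-based figure beside it, that misreading is easy.
2. **Maturity is visible elsewhere.** The OS tables give numbers at risk and confidence intervals at 6, 12, 18 and 24 months, and the main iPFS tables give them at 3, 6 and 12 months. Both are on the endpoint's own scale, and events and censored cases are counted too. This stands in part: these columns protect a careful reader but do not replace a follow-up median.
3. **The timetable limits the risk for OS.** If closure comes 24 months after the last inclusion and survival is followed until then, every survivor not lost has at least 24 months of OS follow-up. This also stands. It is weaker for iPFS, because imaging follows local practice after 12 months.
4. **The effect may be trivial.** If diagnosis means the current stage IV melanoma, the interval could be short, and a 1-month median interval adds only 1 to 2 months. The documents cannot exclude this.

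A reader might infer more than the text supports:

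- **That every time-to-event endpoint starts at inclusion or first dose.** It does not: duration of intracranial response starts at the first documented CR or PR (protocol 10.2).
- **That the overstatement equals the median diagnosis-to-treatment interval.** That holds for a constant interval, but not in general for a reverse Kaplan-Meier median.
- **That immature survival data will be presented as mature.** No follow-up value is reported, and points 2 and 3 count against it.

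**Conclusion.** The mismatch of origins is plain in the text. Followed as written, the SAP would report a follow-up median that includes pre-study time and would give none from inclusion.

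The size cannot be settled from the documents. Against about 42 months from inclusion, the diagnosis-based median runs from 43–44 months to about 54, or to 69–107, depending on the assumed interval and its spread. These figures rest on uniform accrual, exponential survival and no loss to follow-up. They also depend on which diagnosis is meant, and leaving that undefined is a defect of its own.

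The consequence is limited to a misleading descriptive summary. The estimates of OS, iPFS, ePFS and intracranial response, and their intervals, are unaffected. So is the primary endpoint, which is assessed at day 56. The documents do not support a claim that the efficacy results are biased or immature.

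**What to change.** - Compute Tables 48–50 from inclusion (first dose), the same origin as OS and iPFS, and relabel them.
- Make the reverse Kaplan-Meier median in Table 50 the headline figure.
- State the OS origin in SAP 4.5, and say which date is used where inclusion and first dose differ, so that endpoint and follow-up share one definition.
- Keep time since diagnosis only as the baseline characteristic in Tables 13–14 (first diagnosis) and 23–24 (current melanoma).

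The cost is one date variable in the analysis program, three table labels and a sentence in the SAP. No new data are needed. If the program already counts from inclusion and the labels are left over from a template, only the labels need correcting.
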